3. SELECTION OF STUDY POPULATION

3.1. Inclusion Criteria

All participants must meet the following inclusion criteria:

1. Male or female study participants with Sickle Cell Disease:
 - Documentation of SCD genotype (HbSS, HbSC, HbS β thalassemia or other sickle cell syndrome variants) may be based on history of laboratory testing or must be confirmed by laboratory testing during screening.
2. Participants have had at least 1 episode of VOC in the past 12 months. For study eligibility, VOC is defined as a previously documented episode of ACS or acute painful crisis (for which there was no explanation other than VOC) which required prescription or healthcare professional-instructed use of analgesics for moderate to severe pain (documentation must exist in the patient medical record prior to Screening).
3. Age 12 to 65 years (refer to [Section 2.1.1](#)).
4. Hemoglobin (Hb) ≥ 5.5 and ≤ 10.5 g/dL during screening.
5. For participants taking hydroxyurea (HU), the dose of HU (mg/kg) must be stable for at least 90 days prior to signing the ICF and with no anticipated need for dose adjustments or initiation during the study, in the opinion of the Investigator.
6. Participants must demonstrate 75% compliance with ePRO measure completion to be randomized (participants will be given an ePRO device for at least 28 days during Screening). Participants who have <75% compliance may be rescreened up to two times for ePRO compliance.
7. Participants, who if female and of child bearing potential, are using highly effective methods of contraception from study start to 30 days after the last dose of study drug, and who if male are willing to use barrier methods of contraception, from study start to 30 days after the last dose of study drug.
8. Participant has provided documented informed consent or assent (the informed consent form [ICF] must be reviewed and signed by each participant; in the case of pediatric participants, both the consent of the participant's legal representative or legal guardian, and the participant's assent must be obtained).

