8.4.6. Safety and Tolerability Analyses

Safety analysis will be performed on all participants receiving at least one dose of study drug.

A treatment-emergent adverse event (TEAE) is defined as an AE that emerges on or after initiation of study drug (having been absent pretreatment), or an AE that existed pretreatment and worsened on treatment (relative to the pretreatment state). The incidence of TEAEs will be tabulated by system organ class (SOC), preferred term, severity and relationship to study drug.

AEs considered to be related by the Investigator will be summarized. Changes in laboratory parameters and vital signs over time will be summarized. Exposure-adjusted analyses may be performed to account for differences in exposure to study drug between treatment arms.

AEs will be reported by severity and relatedness to study treatment and classified according to Medical Dictionary for Regulatory Activities (MedDRA).

BPs, HR, and clinical laboratory data (hematology, serum biochemistry and coagulation) will be summarized.

For the laboratory safety data, out of range values will be flagged in the data listings and a list of clinically significant abnormal values will be presented.

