APPENDIX A. SCHEDULE OF ASSESSMENTS

Assessments	Screening	Treatment Period												Follow-Up EOS (last dose + 4 Wks)	
		D 1 ^a	W 2 ^b	W 4	W 6 ^b	W 8	W 12	W16 & W20	W 24	W 36	W 48	W 60	W72 ^c & EOT		
Study Day(s):	-35 to -1														
Informed Consent	X														
ePRO Screening (at least 28 days)	X														
Eligibility Assessment	X	x													
Medication and Medical History	X	x													
Physical Examination ^d	X	x	x	x	x	x	x	x	x	x	x	x	x	x	x
Height ^e	X								x		x		x		x
Weight	X						x		x	x	x	x	x		x
Randomization Assignment		x													
Vital Signs ^f	X	x	x	x	x	x	x	x	x	x	x	x	x	x	x
ECG ^g	X	x		x		x	x	x	x	x	x	x	x	x	x
ePRO SCDS Measure		x	x	x	x	x	x	x	x						
EQ-5D-5L ^{TM h}		x		x		x	x	x	x	x	x	x	x		x
Clinical Global Impression -Change (CGI-C; Groups 1 and 2 only)		x					x		x		x	x	x		
Adverse Events	X	x	x	x	x	x	x	x	x	x	x	x	x	x	x
Concomitant Medications		x	x	x	x	x	x	x	x	x	x	x	x	x	
eDiary		x	x	x	x	x	x	x	x	x	x	x	x	x	x
Hematology ⁱ	X	x	x	x	x	x	x	x	x	x	x	x	x	x	x
Erythropoietin		x					x		x	x	x	x	x		x
Exploratory Assessments ^j		x					x		x	x	x	x	x		x
HbF analysis		x					x		x				x		x
Blood Sample for Pharmacogenomic Analysis (if participant opted in on ICF)		x													
Serum Chemistry ^k	X	x	x	x	x	x	x	x	x	x	x	x	x	x	x
Urinalysis ^l	X														x

Assessments	Screening	Treatment Period													Follow-Up EOS (last dose + 4 Wks)
		D 1 ^a	W 2 ^b	W 4	W 6 ^b	W 8	W 12	W16 & W20	W 24	W 36	W 48	W 60	W72 ^c & EOT		
Study Day(s):	-35 to -1														
Coagulation ^m	X														
Serum Pregnancy Test ⁿ	X														
Urine Pregnancy Test ⁿ		x		x		x	x	x	x	x	x	x	x		x
Serum Virology ^o	X														
Iron Studies ^p	X														
Pharmacokinetic Sampling			x ^q				x ^q	x ^q		x	x	x	x	x	

Abbreviations: D = day; ECG = electrocardiogram; EOS = End of Study; EOT = End of Treatment; ePRO = electronic patient reported outcomes; EQ-5D-5L™ = EuroQol EQ-5D-5L™ health questionnaire; HbF = hemoglobin fetal; ICF = informed consent form; SCDS = sickle cell disease severity; W = week; Wks = weeks.

Note: Study visits must be conducted within ± 2 days of the scheduled visit through Week 8, and ± 5 days through Week 24, and ± 7 days for the subsequent visits through EOT; the EOS visit should be completed at 4 weeks (± 7 days) after last dose of study drug.

- a Day 1 assessments should be performed at least 30 minutes prior to study drug administration and may be performed on Day -1.

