- k Serum chemistries will be performed through a central laboratory and will include: Alanine aminotransferase (ALT), albumin, alkaline phosphatase (ALK), aspartate aminotransferase (AST), bicarbonate, blood urea nitrogen (BUN), chloride, calcium, creatinine, glucose, LDH, sodium, potassium, magnesium, phosphorus, unconjugated bilirubin (total, direct, and indirect), and creatine kinase (analyzed as clinically indicated). Calcium, magnesium, phosphorous collected at screening and EOS, and as clinically indicated.
- l Urinalysis will include assessment for color and appearance and dipstick analysis for: Specific gravity, pH, protein, glucose, ketones, leucocytes, bilirubin, urobilinogen, nitrite, creatinine, and occult blood. Collected at screening, EOS and as clinically indicated. Microscopic analysis (RBCs, WBCs, microalbumin, bacteria, and casts) as clinically indicated.
- m Coagulation will include: Prothrombin time (PT), partial thromboplastin (PTT), and international normalized ratio (INR).
- n Serum pregnancy test will be performed during Screening for all female participants of child-bearing potential who are not post-menopausal or surgically sterile. Further pregnancy tests will be urine pregnancy tests. If a urine pregnancy test is positive, the result must be confirmed with a serum pregnancy test.
- o Serum virology will be performed through a central laboratory and will include: Hepatitis B surface antigen (HBsAg), hepatitis A IgM, and hepatitis C virus (HCV) antibody (to be conducted at Screening only, if clinically indicated).
- p Iron studies will include: Serum ferritin, iron and transferrin calculated (% transferrin saturation).
- q Semi-intensive PK samples will be collected in the first 60 participants (Group 1) at Weeks 2, 8 and 12. Semi-intensive PK samples will be collected at predose, between 1 to 4 hours and between 6 to 8 hours. All other participants will have predose PK samples collected, regardless of participation in the semi-intensive PK schedule.

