The Clinical Global Impression of Change (CGIC) is a 7-point scale that requires study medical personnel to assess clinically meaningful change in a participant's sickle cell disease. The rating scale is as follows:

- Very much improved
- Moderately improved
- Minimally improved
- No change
- Minimally worse
- Moderately worse
- Very much worse

CGIC is assessed at Week 24, Week 48, End of Treatment (EOT), and End of Study (EOS).

Incidences of VOC, RBC Transfusion, ACS or Pneumonia On Study

Cumulative incidences of each named event is defined as the number of events from date of randomization to end of study, inclusive.

Time (in weeks) to First VOC

Time to first VOC during the study is defined as

$$(\text{Date of First VOC On Study} - \text{Date of Randomization} + 1) / 7.$$

Subjects who do not have a VOC will be censored at the end of study.

Time (in weeks) to First RBC Transfusions

Time to first RBC transfusions during the study is defined as

$$(\text{Date of First RBC transfusion On Study} - \text{Date of Randomization} + 1) / 7.$$

Subjects who do not have an RBC transfusion will be censored at the end of study.

Time (in weeks) to First ACS or Pneumonia

Time to first ACS or Pneumonia during the study is defined as

$$(\text{Date of First ACS or Pneumonia On Study} - \text{Date of Randomization} + 1) / 7.$$

Subjects who do not have an ACS or pneumonia will be censored at the end of study.

Adverse Event

An AE is defined as any untoward medical occurrence in a subject administered a pharmaceutical product during the course of a clinical investigation. For greater details, refer to Protocol Section 9.1.1.

All adverse events will be recorded on the Adverse Event CRF.

For this study's definition of a Serious Adverse Event (SAE), please refer to Protocol Section 9.1.2.

Treatment-emergent Adverse Event

A treatment-emergent adverse event (TEAE) is defined as an AE that emerges on or after initiation of study drug (having been absent pre-treatment), or an AE that existed pre-treatment and worsened on treatment (relative to the pre-treatment state) through 28 days after study drug discontinuation.

Treatment-emergent Laboratory Abnormalities

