A Treatment-emergent Laboratory Abnormality is defined as any post-baseline laboratory assessment that emerges on or after initiation of study drug through 28 days after study drug discontinuation, which demonstrates an increase of 1 grade or more from the baseline toxicity value. If the baseline value is missing, any graded abnormality (grade 1 or higher) that occurs following initiation of study drug through 28 days after study drug discontinuation is deemed treatment-emergent.

Concomitant Medications

Concomitant medications are those medications taken on or after the initiation of study drug. This definition includes medications started prior to the initiation of study drug but continue concurrently with study drug.

Prior Medications

Prior medications are those medications taken prior to the initiation of study drug.

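### The treatment-emergent laboratory window closes at day 28, but a compliant End of Study sample may be drawn up to day 35

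*SAP*

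**What the plan says.** **SAP section 4, treatment-emergent laboratory abnormalities.** A post-baseline result qualifies from the start of study drug "through 28 days after study drug discontinuation, which demonstrates an increase of 1 grade or more from the baseline toxicity value". If baseline is missing, any graded abnormality "that occurs following initiation of study drug through 28 days after study drug discontinuation is deemed treatment-emergent". The adverse-event definition in the same section has the same upper limit, "through 28 days after study drug discontinuation".

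**Protocol Appendix A.** The last column is headed "Follow-Up EOS (last dose + 4 Wks" and is marked for both hematology and serum chemistry. The note to the schedule says that "the EOS visit should be completed at 4 weeks (± 7 days) after last dose of study drug". The synopsis and protocol section 2.1.6 give the same allowance.

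**Protocol section 4.10.2 and the chemistry footnote to Appendix A.** For three analytes the schedule is sparse: "Calcium, magnesium, phosphorous collected at screening and EOS, and as clinically indicated".

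**SAP section 8.3.4.** The number and percentage of subjects with treatment-emergent graded abnormalities are tabulated by treatment group. The section also provides a shift summary to Week 24, descriptive statistics for named analytes at each evaluation, and a listing of increases of one grade or more.

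**The concern.** A laboratory value exists only for the day the sample is taken. A site can follow the visit schedule exactly, draw the EOS sample on day 30 after the last dose, and obtain a newly graded value that the SAP definition does not admit. The same value drawn on day 27 would count. Both days are within protocol, so the by-arm incidence of treatment-emergent abnormalities depends partly on appointment dates.

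What is at stake is one safety table. It can miss findings from the post-treatment sample, which by design comes only from participants who have stopped study drug. The gap matters most for calcium, magnesium and phosphorus, because no other scheduled post-baseline sample could bring them into the table.

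**Working it through.** **Inputs.** Treatment-emergent limit: 28 days after study drug discontinuation (SAP section 4). EOS visit: 28 ± 7 days after the last dose (Protocol Appendix A).

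**1. The plan's own figure that depends on EOS timing.** Protocol section 2.1.6 gives total participation of about 10 to 81 weeks.

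- Maximum: (35 screening + 72 × 7 treatment + 28 to EOS) / 7 = 567 / 7 = 81.0 weeks.
- Minimum: (28 + 2 × 7 + 28) / 7 = 70 / 7 = 10.0 weeks.

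Both reproduce with EOS at the nominal day 28. With the 7-day allowance the maximum would be 574 / 7 = 82.0 weeks. The stated range therefore does not include the late side of the visit allowance.

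**2. Permitted EOS days.** 28 − 7 = 21 to 28 + 7 = 35, which is 35 − 21 + 1 = 15 days.

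**3. Permitted days after the limit**, taking discontinuation as the last dose:

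| Window closes, days after last dose | EOS days outside | Share of permitted days |
|---|---|---|
| 28 (ordinary reading) | 29–35 | 7/15 = 47% |
| 29 (day count one day more generous) | 30–35 | 6/15 = 40% |
| 35 (aligned with the visit allowance) | none | 0/15 |

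If discontinuation is dated k days after the last dose, the limit moves to day 28 + k and the number of days outside is max(0, 7 − k). The gap closes only when k is 7 or more.

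**4. Where a late EOS value still appears (SAP section 8.3.4).**

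- Treatment-emergent table by arm: governed by the definition, so the value is left out.
- Shift summary: runs only through Week 24, so it does not take in an EOS visit after that.
- Descriptive statistics: not tied to day 28, but limited to 11 named analytes (6 hematology, 5 chemistry). Calcium, magnesium and phosphorus are not among them.
- Listing of increases of one grade or more: not tied to day 28, so the value is kept.

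**5. Whether another rule closes the gap.** SAP Table 1 assigns samples to nominal visits by study day. It has no EOS row and does not address treatment-emergent status. Nothing in section 8.3.4 brings a day 29–35 sample into the window.

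**The case against.** The strongest reply is that this is narrow and the data are not lost. Much of that stands. An abnormality already graded by day 28 counts whatever happens later, and late values reach the listing and, for the named analytes, the descriptive statistics. Participants still on treatment at the 31 October 2018 cutoff have no EOS sample to lose in the primary analysis. The SAP also does not define the discontinuation date, and section 4 separates end of treatment from last date of dosing, so the gap could be smaller than 7 days. What remains is that the by-arm table omits a compliant, scheduled sample and no text says this is intended.

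A reader might infer more than the documents support:

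- *That nearly half of EOS panels are lost.* The 47% is a share of permitted days. The target is day 28, and nothing supports an even spread over the allowance.
- *That adverse events are affected in the same way.* Their status follows onset date, not visit date. SAP section 8.3.3 imputes missing onset dates for this purpose, so an event starting on day 20 and reported on day 35 counts. Extending that window has its own cost: a participant last seen on day 21 would have 35 − 21 = 14 unobserved days inside it, against 28 − 21 = 7 now.
- *That the SAP contradicts the protocol.* Protocol section 8.4.6 has no upper limit ("A treatment-emergent adverse event (TEAE) is defined as an AE that emerges on or after initiation of study drug"), but Protocol section 8 and SAP section 2 let the SAP supersede. Adding a limit is a permissible specification.
- *That the contraception period, "from study start to 30 days after the last dose of study drug", shows exposure is relevant beyond day 28.* The criterion makes no link to event attribution, and it would not support 35 days.
- *That the EOS visit exists to catch withdrawal or delayed effects.* The documents schedule the visit without stating a purpose.

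**Conclusion.** The mismatch is real and confined to the treatment-emergent laboratory table. On the ordinary reading that discontinuation is the last dose, 7 of the 15 permitted EOS days fall outside the window (6 of 15 under a more generous day count). Only an abnormality first seen, or first worsened by a grade, on those days is omitted. The number of participants affected cannot be derived, because the documents give no actual EOS dates.

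The effect is clearest for calcium, magnesium and phosphorus, where a late EOS visit removes the only scheduled post-baseline sample from any treatment-emergent count. This assumes that the grading sentence in SAP section 8.3.4 is not restricted to the analytes in its descriptive list. The text does not restrict it.

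The 28-day limit for adverse events is not an error. Efficacy, alpha and power are untouched. This is a minor point of safety tabulation, worth correcting because the correction is simple.

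**What to change.** In both sentences of the treatment-emergent laboratory definition in SAP section 4 (baseline present and baseline missing):

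- Anchor the window to the date of the last dose instead of an undefined discontinuation date.
- Include laboratory assessments through the EOS visit, up to 35 days after the last dose.
- End the window before any first dose of open-label voxelotor (the extension is described in Protocol section 2.1.5), so that extension results are not attributed to the randomized arm.

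This leaves 0 of the 15 permitted EOS days outside the window. Aligning the adverse-event limit to 35 days is optional.

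The cost is two sentences of SAP wording and one derivation rule. The downside is up to 35 − 28 = 7 more off-drug days per participant, counted by the same rule in all arms. If the sponsor prefers to keep 28 days, the SAP should say that excluding later EOS samples is intended, and tabulate abnormalities from days 29–35 separately by arm.

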5. STUDY ENDPOINTS

Primary Endpoint:

The primary efficacy measure is Hb response at Week 24, as defined in [Section 4](#).

Secondary Endpoints:

The secondary efficacy endpoints are as follows:

- Change from baseline in hemoglobin at Week 24
- Change and percent change from baseline in hemolysis measures, including unconjugated bilirubin, absolute reticulocyte, reticulocytes %, and LDH
- Annualized incidence rate of VOC

Exploratory Endpoints:

- Change from baseline in hemoglobin at Week 48 and Week 72
- Change and percent change from baseline in hemolysis measures: including unconjugated bilirubin, absolute reticulocytes, reticulocytes %, and LDH, at Week 48 and Week 72
- Time to first VOC
- Time to first ACS or pneumonia
- Time to first RBC transfusion
- Rate of opioid use as recorded in the eDiary
- Sickle Cell Disease Severity Measure (SCDSM)
- EuroQol EQ-5D-5L™ health questionnaire (EQ-5D-5L™)
- Clinical Global Impression Scale (CGI)
- School and/or work attendance as recorded via eDiary

6. GENERAL STATISTICAL CONSIDERATIONS

6.1. Sample Size and Power

The sample size for the primary analysis of the study, including both Groups 1 and 2, is 274 randomized subjects. All randomized subjects will be included in the efficacy analysis.

For the primary analysis of hemoglobin response rate comparing voxelotor 1500 mg to placebo, assuming a 10% Hb response rate in placebo, the study with approximately 90 subjects per treatment group will have >95% power to detect a targeted difference of 30%, using Fisher's exact test with a two-sided alpha of 0.0481.

6.2. Randomization and Unblinding

Randomization was carried out centrally through an IXRS. Permuted blocks within randomization strata were used. At the time of randomization, subjects were stratified for hydroxyurea (HU) use (yes/no), geographic region (North America, Europe, Other), and age (adolescent, 12 to <18 years, and adults, 18 to 65 years).

This study is designed as a double-blinded study. The voxelotor and placebo capsules or tablets were matched for shape, size, and color.

To facilitate the Group 1 and 2a Analyses, certain Sponsor representatives and Sponsor designees were unblinded to treatment assignments prior to and during the analysis (including the biostatistics contract research organization [CRO], Sponsor Biostatistics and Programming staff, and external groups for bioanalytical PK/PD). However, except for those noted above, the rest of the Sponsor study team, including all study team members who have direct interactions with study sites, was not unblinded to individual treatment assignment. No site staff or study subjects were unblinded to randomization assignment.

6.3. Handling of Data

6.3.1. Strata

Unless otherwise specified, analysis of data from subjects in Groups 1 and 2 combined will be adjusted for the randomization stratification factors.

For Group 2b analysis, due to the small sample size of n=118, adjustment for the randomization stratification factors will be made only for a single stratification factor. The stratification factor that will be used in the Group 2b analysis is HU use at baseline.

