6.3.2. Examination of Subject Subsets

Subgroups defined by subject age group, (adolescent, 12 to <18 years; and adults, 18 to 65 years), geographic region (North America, Europe, Other), baseline HU use (yes, no), baseline VOC history (1, >1) will be analyzed to evaluate the internal consistency of the study outcomes. Subgroups defined by baseline Hb level will also be explored.

In addition, comparability of study cohorts (e.g., Group 1, Group 2a, Group 1 & 2a, and Group 2b) will be assessed. Specifically, descriptive statistics will be presented for each study cohort regarding the following:

- Demographics
- Baseline disease characteristics
- Subject disposition by study visit
- Rates of missing Hb assessment at Week 24

Hb response rate and Hb change from baseline in voxelotor treatment groups compared to placebo will also be summarized by study cohort.

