8.2.1.2. Additional Analysis of Hb

Change from baseline in Hb over time up to Week 24 will be analyzed using a mixed effect for repeated measures (MMRM) model. The fixed effect terms include treatment, study visit, treatment by visit interaction, HU use at baseline, age group and geographic region. Baseline Hb will be a co-variate. Within-subject variability will be modeled using an unstructured covariance matrix. Missing data due to early drop out or missed visit will not be imputed for this analysis. Missing data due to VOC, VOC hospitalization or RBC transfusion will be imputed, as described in [Section 6.3.5](#).

Change from baseline in hemoglobin up to Week 48 and Week 72 will be analyzed similarly with available data as of the clinical cutoff date for the primary analysis.

The adjusted mean (lsmean) change from baseline in Hb at each visit, estimated from the MMRM model, with the estimated standard error and 95% confidence interval (CI), will be presented in tabular and graphic format. The difference in the adjusted means between treatment groups and the associated 95% CI of the difference will be provided.

Hb worsening will be summarized using a shift table for each treatment group. Incidences of post-baseline Hb < 5.5 g/dL will be summarized by treatment group, as well as incidences of Hb change from baseline < -2 g/dL.

Proportion of subjects with Hb of ≥ 10 g/dL at Week 24 will be explored.

All analyses specified above will be based on data with imputation for RBC transfusion, VOC and VOC hospitalization, as applicable. The analysis of Hb response rate will also be repeated using observed data without imputation to assess the robustness of the data.

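### The Group 2b Hb-change analysis need not drop age and region: small n is no reason in a linear model, and the adjustment then differs from the combined analysis (minor)

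*SAP*

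**What the plan says.** - **Randomization (SAP 6.2).** "At the time of randomization, subjects were stratified for hydroxyurea (HU) use (yes/no), geographic region (North America, Europe, Other), and age". On the method: "Permuted blocks within randomization strata were used". The factors have 2, 3 and 2 levels, giving 12 strata.
- **Combined analysis (SAP 6.3.1 and 8.2.1.2).** Groups 1 and 2 together are adjusted for the randomization factors. For the Hb-change MMRM: "The fixed effect terms include treatment, study visit, treatment by visit interaction, HU use at baseline, age group and geographic region". Baseline Hb is a further covariate.
- **Group 2b (SAP 6.3.1).** The rule is narrower: "due to the small sample size of n=118, adjustment for the randomization stratification factors will be made only for a single stratification factor". The factor is then named: "The stratification factor that will be used in the Group 2b analysis is HU use at baseline".
- **Role of Group 2b (SAP 2 and 6.3.2).** These are the Group 2 subjects not unblinded at the interims. They are analysed for comparability with Groups 1 and 2a, and the SAP is to be finalised before they are unblinded. On presentation: "Hb response rate and Hb change from baseline in voxelotor treatment groups compared to placebo will also be summarized by study cohort".
- **Group 1 (Protocol 8.4).** There is also a single-factor rule for Group 1, again because of its size. The factor there is chosen by balance between strata levels, so it need not be HU use.

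The SAP does not say whether the HU-only rule covers the response rate, Hb change or both. It states no power, precision or interval for Group 2b.

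**The concern.** When randomization is blocked within factors that are related to the outcome, the treatment estimate is already more precise than a model without those factors can recognise. The model-based standard error is then too large, and the interval covers more often than its nominal level. Including the factors avoids this. Sample size is a good reason to leave them out only if they are expensive to include.

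What is at stake is a consistency check. Group 2b is the one cohort whose data were still blinded when the SAP was to be finalised, and its results are to be set beside those of Groups 1 and 2a. If Group 2b is adjusted for HU use alone and the combined analysis for three factors, part of any difference in estimate or width could come from the model and not from the cohort.

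**Working it through.** **Plan's own figure.** The documents give none for Group 2b. The nearest is the power of the primary comparison in SAP 6.1: 40% against 10%, about 90 per arm, Fisher's exact test, two-sided alpha 0.0481. Exact enumeration gives 99.7%, consistent with the stated figure of more than 95%.

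**Inputs from the documents.** n = 118 randomized 1:1:1, so 118/3 = 39.3 per arm (SAP 2). SD 0.6 g/dL and effect 0.8 g/dL, the Group 1 planning values (Protocol 8.2.1). Adolescents 46/274 = 17% (SAP 2).

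**Assumption.** R² is the share of residual variance explained by age and region, given the other terms in the model. The documents give no value, so a range is shown.

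**Step 1: cost in degrees of freedom.** Age takes 1 and region 2. For a two-arm contrast, half-width = t × SD × √(2/n), with √(2/39.33) = 0.2255.

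- HU only, 75.7 df: 1.9918 × 0.6 × 0.2255 = 0.269 g/dL.
- Age and region added with no explanatory value, 72.7 df: 1.9932 × 0.6 × 0.2255 = 0.270 g/dL.

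The cost is about 0.1% of width. The simulation in step 3, which also picks up chance imbalance, puts it at 0.4%.

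**Step 2: possible gain.** With the factors included, the SD becomes 0.6 × √(1 − R²). The ratio of widths does not depend on the SD.

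| Assumed R² | HU only | With age and region | Ratio |
|---|---|---|---|
| 0% | 0.269 | 0.270 | 0.999 |
| 2% | 0.269 | 0.267 | 1.009 |
| 5% | 0.269 | 0.263 | 1.025 |
| 10% | 0.269 | 0.256 | 1.053 |
| 20% | 0.269 | 0.241 | 1.117 |

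**Step 3: check by simulation.** 4,000 trials per setting used a single-visit linear model as a stand-in for the MMRM, with 12 strata. Assumed: blocks of 6, HU use 60%, region shares 40/20/40, and R² split equally between age and region. Each stratum started mid-block, because Group 2b follows earlier enrolment.

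| Assumed R² | Width ratio | Coverage, HU only | Coverage, all three |
|---|---|---|---|
| 0% | 0.996 | 94.9% | 95.0% |
| 5% | 1.021 | 95.6% | 95.2% |
| 10% | 1.051 | 95.6% | 95.0% |
| 20% | 1.115 | 96.2% | 94.8% |

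The Monte Carlo standard error of a coverage figure is √(0.95 × 0.05/4000) = 0.3 percentage points. The mean HU-only estimate was 0.798 to 0.803 g/dL across settings, against a true 0.8, so there is no bias.

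**Step 4: the responder analysis.** A stratified exact test is a different case. A two-arm comparison in Group 2b has 118 × 2/3 = 78.7 subjects, or 78.7/12 = 6.6 per stratum. The combined data have 274 × 2/3/12 = 15.2. Simulated exact CMH power at 40% against 10%, about 39 per arm (1,500 runs), was 87.7% with HU only and 85.7% with 12 strata when age and region were not prognostic. It was 86.2% and 85.5% when they were. The small-sample reason has some force here.

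**Step 5: scale.** At R² = 5% to 10% the excess half-width is 0.006 to 0.013 g/dL, against a planning effect of 0.8 g/dL. Sample size matters far more: the half-width is 0.269 at n = 118 and 0.175 at n = 274.

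**The case against.** The strongest reply is that nothing confirmatory depends on this. Group 2b has no place in the fixed sequence of SAP 6.3.3. The primary test and the nine secondary hypotheses use all 274 subjects with full adjustment. The estimate is unbiased and any error in the interval is on the conservative side. All of that stands, and it limits the point to a minor one.

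A second reply is that the SAP names no Group 2b interval, since SAP 6.3.2 speaks only of summaries by cohort. That stands as a caveat. But an adjustment rule has meaning only if a model or stratified test is run, and SAP 2 says that the document covers the analysis of Group 2b data. If the rule is meant for the response rate alone, the SAP should say so.

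Two stronger readings are tempting, and the documents do not support them:

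- A reader might infer that the Group 2b Hb-change intervals are too wide as a matter of fact. That requires age and region to predict Hb change after HU use and baseline Hb. The documents give no figure for this, and if they predict nothing the HU-only interval is slightly the narrower.
- A reader might infer that Group 2b was singled out while smaller cohorts escaped restriction. Protocol 8.4 already applies a single-factor rule to Group 1 on the same ground. What remains is that the factors are chosen differently, and that neither document states a rule for Group 2a alone.

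**Conclusion.** The point holds in a limited form. Small sample size does not justify leaving age and region out of a linear model of Hb change in 118 subjects, because including them costs less than 0.5% of interval width. Leaving them out introduces no bias. It may give an interval about 2.5% wider than necessary at R² = 5% and 5% wider at 10%, with coverage slightly above nominal. It also makes the Group 2b adjustment differ from that of the combined MMRM.

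The sizes rest on assumed R² values, equal arms, assumed block size and HU and region shares, and a single-visit stand-in for the MMRM. The effect on any conclusion is small, because Group 2b is supportive and carries no alpha. This is a free or cheap improvement, of minor weight.

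**What to change.** In SAP 6.3.1, before Group 2b is unblinded:

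1. Limit the HU-only rule to the stratified exact CMH analysis of Hb response in Group 2b.
2. For any Group 2b Hb-change MMRM, use the covariates of SAP 8.2.1.2: HU use, age group and region as additive fixed effects, with baseline Hb.
3. Use the same covariate set for the other cohort Hb-change models shown beside it, and state that for this display it replaces the single-factor rule of Protocol 8.4. If a factor level is empty in a cohort, footnote it.

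The cost is a sentence or two and a changed model statement; the statistical price in Group 2b is 3 degrees of freedom. A single MMRM on all 274 subjects with cohort interactions is not needed. It would estimate covariance and covariate effects partly from subjects already unblinded, so Group 2b would no longer stand alone as a check.
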